# Remote glucose monitoring using the Dexcom G6 Continuous Glucose Monitoring (CGM) System in hospitalized patients with diabetic ketoacidosis (DKA)

Study Purpose and Rationale:

We propose to study use of Continuous Glucose Monitoring (CGM)for glucose monitoring in patients with DKA which would enable the treatment of hemodynamically stable DKA patients outside of intensive care units (ICU) thereby saving ICU beds a precious resource which have become extremely scarce resource during COVID-19 pandemic (1). In most hospitals, protocols for treatment of patients with diabetic ketoacidosis (DKA) require capillary point of care (POC) glucose testing every 1-2 hours (2) . Often, patients need to be transferred to the intensive care units (ICU) for frequent fingerstick glucose monitoring in order to safely administer intravenous insulin to treat the DKA. During the COVID-19 pandemic, this need to transfer patients to the intensive care unit (ICU) for treatment of DKA and the requirement for nurses to enter the room every 1-2 hours has contributed to scarcity of critical care unit beds and shortage personal protective equipment (PPE) Additionally, COVID-19 patients have been prone to develop DKA which has further increased the need for ICU beds (3, 4). Therefore, methods to safely and effective treat patients with DKA outside of ICU setting represent a common and pressing need.

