#### **Prospective Study**

The prospective part of this study will involve recruiting patients in the Emergency Department and offering them the opportunity to use DEXCOM G6 CGM instead of hourly fingerstick point of care glucose testing . We will enroll additional 50 non-critically ill DKA patients who will have glucose levels monitored via DEXCOM CGM and be treated in the stepdown unit. The primary outcome is time to resolution of metabolic acidosis. Secondary outcomes are length of ICU stay, length of hospital stay, frequency of hypoglycemic episodes defined as glucose level <70 mg/dl and cost savings.

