# Statistical Procedures:

The primary outcome for this study is the time to resolution of DKA. We will compare time to resolution of the DKA of patients who had glucose levels monitored via DEXCOM G6 CGM and treated in the stepdown unit (both those enrolled in the retrospective study and those who will be enrolled in the prospective study) to DKA patients who had glucose levels monitored hourly via fingerstick (and not CGM) and treated in the ICU setting.

We will perform a non-inferiority trial to study whether monitoring glucose levels via CGM in DKA patients treated in the stepdown unit is not inferior to DKA treated patients in the ICU setting with hourly fingerstick glucose monitoring.

For a noninferiority trial, based on what we have previously observed for the time to resolution of DKA, and a noninferiority margin of 1/2 the SD, we estimate that a sample size of 98 patients per group will have a 90% power to determine noninferiority at an alpha level of 0.05. Since we enrolled 48 patients in the retrospective part of the study, we will need additional 50 patients enrolled in the prospective part of the study to have 90% power and a noninferiority at an alpha level of 0.05. We plan a conservative approach where we will enroll additional 50 DKA patients who will have glucose levels monitored via CGM. We will compare with the historical control using 1:1 matching, thus will collect historical control data which include DKA patients treated for DKA in the ICU setting with hourly fingerstick glucose monitoring.

We will perform linear regression (for patients enrolled in both retrospective and prospective part of the study) to learn what clinical factors are associated with length of time to the DKA resolution. Then we will use propensity matching for historical control group (DKA patients treated in the ICU setting with glucose levels monitored via hourly fingerstick glucose levels).

To study the frequency of hypoglycemic episodes (<70 mg/dl) in patients from both prospective and retrospective study; we will use CGM glucose data stored manufacture's web based software : Clarity.

We will also evaluate frequency of hypoglycemic episodes (glucose level <70%) in historical control patients who were treated for DKA in the ICU and had hourly glucose level monitoring.

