- 3. Once glucose levels are transmitted to the study smartphone devices, glucose levels from the CGM to guide insulin adjustments. Check fingerstick glucose if CGM glucose levels are <100 mg/dl and >350 mg/dl to guide treatment decisions. Note that CGM device will have audible alerts if glucose level are < 100 mg/dl and >350 mg/dl. If there are NO glucose levels transmitted to the phone please check q 1 fingerstick glucose levels and contact [name] ([name]). If CGM glucose data cannot restored and patient needs g 1 hour fingerstick glucose testing, patient will be transferred to the ICU. If patient is moved to the ICU the CGM will be removed. Although CGM data will be transmitted to the study smartphone devices continuously, please monitor CGM glucose levels every 1 hour and make treatment decisions based on q 1-hour CGM readings or more frequently when glucose levels are <70 mg/dl (confirmed with a fingerstick glucose). If patient's glucose levels are <100 mg/dl on the CGM, fingerstick glucose testing will be performed to ensure that fingerstick glucose level is not in hypoglycemic range (<70 mg/dl). If patient's glucose levels are in hypoglycemic range (<70 mg/dl), fingerstick glucose levels testing will be performed as per hospital protocol until hypoglycemia resolves. Once hypoglycemia resolves, then glucose levels from the CGM can be used for further insulin adjustments. In the Emergency Department, document glucose levels q 2 hours as per the research protocol or more frequently as per provider request treating the patient. When patient is transferred to the stepdown unit, glucose levels should be recorded every 3 hours in hospital electronic medical record system.
- 4. If the patient condition worsens and patient requires the ICU care, patient will be transferred to the ICU. Also, if patient needs to get MRI or CT, sensor and transmitter will be removed prior to the imaging.
- 5. Smartphones which are receiving glucose data (study provider smart phone, study nurse smart phone and the study patient smart phone which receives glucose level from the sensor and is next to the IV insulin bag) should be transferred to the Stepdown Unit nurse when patient is arrives at the Stepdown Unit.

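### ICU transfer of CGM patients is neither an outcome nor given an analysis rule, so non-inferiority could be declared, and ICU care called unnecessary, despite a material transfer rate

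*Combined protocol and SAP*

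**What the plan says.** The Study Purpose and Rationale gives the motive: "methods to safely and effective treat patients with DKA outside of ICU setting represent a common and pressing need". It then sets out the inference. If CGM is non-inferior on time to resolve DKA and on hypoglycemia, hemodynamically stable, non-intubated patients could be managed in stepdown instead of being moved to the ICU.

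Study Procedures, Prospective Study, describes two ways in which stepdown care ends in the ICU.

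- Item 4, clinical worsening: "If the patient condition worsens and patient requires the ICU care, patient will be transferred to the ICU".
- Item 3, loss of the CGM signal: "If CGM glucose data cannot restored and patient needs g 1 hour fingerstick glucose testing, patient will be transferred to the ICU".

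Item 3 adds: "If patient is moved to the ICU the CGM will be removed". A transferred patient therefore moves to the setting and monitoring of the comparator.

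Statistical Procedures states: "The primary outcome for this study is the time to resolution of DKA". In Study Design, Prospective Study, the remaining outcomes are: "Secondary outcomes are length of ICU stay, length of hospital stay, frequency of hypoglycemic episodes defined as glucose level <70 mg/dl and cost savings". The retrospective part lists the same ones. ICU transfer is not among them.

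Two passages bear on who is analysed. Statistical Procedures describes the CGM group as patients both monitored by CGM and cared for in stepdown, and does not mention those later moved. Study Design, Retrospective Quality Improvement Data, reports 48 such patients and leaves out 2 more who wore CGM but were treated in the ICU. It does not say whether those 2 began in stepdown.

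**The concern.** The practice claim is about avoiding the ICU. The most direct evidence against it would be the share of patients started on CGM for stepdown care who ended up in the ICU anyway. The plan foresees that event and does not count it.

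The primary outcome reflects transfer only through any delay it causes. If transferred patients are kept, the time to resolution credited to stepdown care includes treatment given in the ICU. If they are left out, as the wording of the CGM group and the handling of the 2 retrospective patients would allow, the failures disappear from the comparison altogether. Under either handling, a report could state non-inferiority and recommend care outside the ICU without saying how often that care had to be abandoned.

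**Working it through.** **The plan's own figure.** Statistical Procedures gives 98 per group for 90% power, a margin of half an SD and alpha 0.05, with sidedness not stated. With a true difference of zero, n = 2 × [(z for alpha + z for power) / 0.5]².

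- One-sided 0.025: 2 × [(1.960 + 1.282)/0.5]² = 84.06, so 85 per group.
- One-sided 0.05: 2 × [(1.645 + 1.282)/0.5]² = 68.5, so 69 per group.

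The 98 is not reproduced, but it exceeds both figures. With 98 the standard error is √(2/98) = 0.1429 SD. Power is Φ(0.5/0.1429 − 1.960) = Φ(1.54) = 93.8%, or 96.8% at one-sided 0.05. The derivation of 98 is a separate matter; I take 98 as given.

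**Case A: transferred patients kept.** Assume a share r is transferred, transfer adds d SD to their time, and all other CGM patients match controls on average. Then:

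- mean shift = r·d
- variance in the CGM group = 1 + r(1 − r)d²
- P(non-inferiority) = Φ[(0.5 − r·d)/√((2 + r(1 − r)d²)/98) − z]

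With r = 20%:

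| Added delay | Shift (SD) | SE (SD) | One-sided 0.025 | One-sided 0.05 |
|---|---|---|---|---|
| 0 | 0 | 0.1429 | Φ(1.540) = 93.8% | 96.8% |
| 0.5 SD | 0.10 | 0.1443 | Φ(0.812) = 79.2% | 87.0% |
| 1 SD | 0.20 | 0.1485 | Φ(0.061) = 52.4% | 64.6% |

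At one-sided 0.025, with delays of 0.5 and 1 SD, r = 10% gives about 88% and 78%, and r = 30% gives about 68% and 26%. With no delay the result is 93.8% whatever the transfer rate.

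**Case B: transferred patients dropped.** Again with 20% transferred, about 78 CGM patients remain. Against 98 controls the standard error is √(1/78 + 1/98) = 0.1517, and the probability is Φ(0.5/0.1517 − 1.960) = 90.9%. If the matched controls are dropped too (78 against 78), it is 87.7%. The delay in transferred patients no longer enters at all. This assumes that the patients who remain match controls on average.

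**What the documents show about the rate.** There is one related count: 2 CGM patients treated in the ICU beside 48 in stepdown. If both were transfers, the rate is 2/50 = 4%, with an exact (Clopper-Pearson) 95% CI of 0.5% to 13.7%.

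**What a direct estimate would give.** With 98 CGM patients, 10 transfers is 10.2% (exact 95% CI 5.0% to 18.0%) and 20 transfers is 20.4% (12.9% to 29.7%). That is precise enough to separate a low transfer rate from a high one.

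**The case against.** Four points can be made on the other side.

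*The primary outcome does respond to transfer.* A reader might infer that a transferred patient simply scores as a success, or that time to resolution is blind to the problem. The documents do not support either reading. The outcome is a duration, so a transferred patient contributes a time, and a long delay counts against CGM: at 20% transferred, a 1 SD delay lowers the probability from 93.8% to 52.4%. This stands. The weakness is confined to transfers that cause little delay, or that are excluded.

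*The plan never says transferred patients are kept.* Correct, and the wording leans towards leaving them out. That changes the route but does not remove the gap, because exclusion conceals failures more completely.

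*Length of ICU stay is already a secondary outcome.* CGM patients are meant to go to stepdown, so a non-zero ICU stay in one of them marks a transfer, and the data collected could yield the proportion. This stands in part. But the measure mixes how many were transferred with how long they stayed, gives no reason and has no margin. It is also compared with controls who were all in the ICU, so the CGM group could look favourable despite many transfers.

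*A 20% rate is speculative.* It is. The exclusion criteria remove patients with hypotension, ventilation, altered mental status or another clinical reason for ICU admission, and the single count available points to a lower rate if it reflects transfers at all. The 20% shows how the analysis behaves; it is not a forecast.

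**Conclusion.** The concern holds in a limited form. ICU transfer is foreseen by two routes, is not an outcome and has no analysis rule, while the intended conclusion is that the ICU is not needed. Non-inferiority on time to resolution can therefore coexist with a material transfer rate. At an assumed 20%, with one-sided 0.025, 98 per group and a 0.5 SD margin, the probability of declaring it is about 94%, 79% or 52% for added delays of 0, 0.5 or 1 SD if patients are kept, and about 88% to 91% if they are dropped. The rates, the delays, the normal approximation and the equality of non-transferred patients with controls are all assumptions.

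It would go too far to infer that many patients will be transferred, or that the 2 retrospective patients were failures of stepdown care; the documents establish neither. The primary comparison can stand. The practice conclusion needs the transfer proportion beside it.

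**What to change.** 1. State in Statistical Procedures that every patient started on CGM for stepdown care stays in the primary analysis, with time to resolution running through any ICU transfer. Account for the 2 retrospective patients under the same rule: include them if they were started on CGM for stepdown care and then transferred, and otherwise say why they fall outside the group.
2. Add ICU transfer during the index DKA episode as a key secondary outcome in the CGM group. Split it by reason (clinical worsening or CGM data loss) where the chart records one, and give an exact 95% CI. Report it beside the primary result wherever treatment outside the ICU is concluded.

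Neither step alters patient management. The cost is slightly more abstraction within the chart review already planned for both parts, plus up to two more matched controls if the 2 patients are included. The reason for transfer may be missing for some retrospective patients and should then be reported as unknown. The headline may look less favourable.

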#### Prospective Study

Patients who have glucose levels monitored by the CGM will be treated in the Stepdown Unit instead of intensive care unit (ICU) setting. Glucose levels from the CGM will be transmitted to the smartphones devices which will be provided to the provider and nurse taking care of the patient by the study team.

We provided extensive training for the ED staff and Stepdown Unit staff regarding the use of CGM in patients with DKA. Additionally, we will provide information sheet describing provider and nurses' role when DKA patients are monitored via CGM.

Once provider and the nurse in the ED give verbal consent for the study, and patient gives a written consent, a research coordinator will attach CGM DEXCOM G6 device (which consists of sensor and transmitter) on patient's arm and set up smartphone devices (study patient smartphone, study provider smartphone and study nurse smartphone) to receive glucose levels from the CGM device.

Description of the remote glucose monitoring via CGM device and workflow:

1. A research coordinator will apply sensor (which senses glucose levels just below the skin from the interstitial fluid) and transmitter (which gets glucose information from the sensor and send glucose information to the DEXCOM G6 app via Bluetooth to the smart phone provided by the study team) on the patient. The Dexcom CGM will be attached to the upper arm or lower abdomen. The patient will be asked for their preference. The Dexcom CGM should not be placed where the patient is lying down or sleeps. CGM will not be placed on scars, hair, tattoos, irritated areas, areas where the sensor can be rubbed (waist band, seat belt), and insulin injection sites. The patient may already be wearing their own personal CGM, which should not be removed. If the patient's personal CGM is on the arm, the study Dexcom CGM will be attached to the lower abdomen. If the patient's upper arm. The study patient smartphone receiving glucose level data needs to be placed on the patient's IV pole next to the insulin bag.

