In order to have glucose levels sent from the transmitter to the DEXCOM app, each patient needs to have a user name and a password. A user name and password for each patient is created by the research team. Patient's information is coded when transmitted to these phones, meaning that instead of referencing any PHI such as MRN to identify the patient, the patient is labeled via a unique study-specific identifier ("study participate 001"). If the phones were to get lost, there will be no concern for improper release of PHI. The "study smartphone for the patient " is placed on the IV pole next to insulin infusion bag.

2. A study coordinator will set app DEXCOM follow apps (which are necessary for glucose to be sent from the patient study phone) on the study smartphones given to the nurse and provider for remote glucose monitoring.

There is a 2 hour "warm up" period until glucose levels are transmitted the study patient smartphone and during that time glucose levels should be checked via hourly fingerstick as per the DKA protocol.

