- 6. Sensors and transmitters are removed on the day of transfer to the hospital ward from the stepdown unit or 10 days from insertion (whichever comes first). The reason the sensors are not be removed at the resolution of DKA is that in case anion gap (AG) reopens (which indicates that patient is in DKA) then we can continue to monitor glucose levels using the sensor in place. Both sensors and transmitters will be removed by the primary nurse. The study smart phones are be returned to the research team (research coordinator) once DKA resolves.

The same process of abstracting data and demographic information described for the retrospective study from the patient's medical records for analysis will be used.

Provider Survey

We will identify nurses via EMR who took care of DKA patients who had glucose levels monitored via DEXCOM G6 CGM. We will then send them e-mail asking to voluntarily participate in the survey. The link to the anonymous QUALITRIC survey will be included in the e-mail.

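### Item 6 keeps the sensor on in case DKA recurs, but returns every phone that could show its readings as soon as DKA resolves

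*Combined protocol and SAP*

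**What the plan says.** The point sits in Study Procedures, Prospective Study, item 6, which sets two different times for taking equipment back.

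- For the worn parts: "Sensors and transmitters are removed on the day of transfer to the hospital ward from the stepdown unit or 10 days from insertion", whichever is earlier. The item explains why this is later than resolution: should the anion gap reopen, "then we can continue to monitor glucose levels using the sensor in place".
- For the phones: "The study smart phones are be returned to the research team (research coordinator) once DKA resolves". No phone is exempted.

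Item 3 of the same section covers loss of signal: "If there are NO glucose levels transmitted to the phone please check q 1 fingerstick glucose levels and contact" the study team. If the data cannot be restored and hourly testing is needed, the patient goes to the ICU and the CGM is removed.

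**The concern.** The event that sends the phones back is the very event the sensor is deliberately kept on beyond. If the phones are the only means of reading the sensor, the second instruction undoes the purpose of the first.

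The patient at issue is one the protocol itself foresees: someone in the stepdown unit who goes back into DKA. That is when frequent glucose readings are needed again, and when the design relies on CGM. Under Retrospective Quality Improvement Data, the protocol explains that hourly fingersticks could be done only in the ICU and not in stepdown. The fallback for a missing signal therefore leans on a practice that the protocol says the unit could not provide, and its end point is the ICU transfer the study is meant to avoid.

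**Working it through.** The plan gives no figure to reproduce. The check sets the instructions of the Prospective Study section side by side.

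1. **From sensor to first phone (item 1).** The transmitter is to "send glucose information to the DEXCOM G6 app via Bluetooth to the smart phone provided by the study team". This is the patient study phone, kept on the IV pole.
2. **From first phone to staff (item 2).** The nurse and provider phones depend on the patient phone: "A study coordinator will set app DEXCOM follow apps (which are necessary for glucose to be sent from the patient study phone"). Without the patient phone, the other two have no described source of readings.
3. **Count of receivers (item 5).** The phones handed over to stepdown are listed as "study provider smart phone, study nurse smart phone and the study patient smart phone which receives glucose level from the sensor". That makes patient + provider + nurse = 3.
4. **Other routes.** Items 1 to 6 describe no bedside receiver and no use of staff members' own phones. A patient's personal CGM may stay on, but nothing says staff would use it. The manufacturer's web software appears only under Statistical Procedures, as the data source for the hypoglycaemia analysis.
5. **Receivers left after resolution (item 6).** 3 described − 3 returned = 0.
6. **Length of the gap.** It starts at DKA resolution and ends when the sensor comes off. The latest end is 10 days × 24 h = 240 h from insertion, so its length is at most 240 h minus the time from insertion to resolution. Ward transfer will end it sooner for some patients, as will the removals in items 3 and 4 (ICU transfer, MRI or CT). The documents give no typical duration.
7. **Re-issue.** No step for bringing phones back or pairing them again is written.

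One detail rests on an assumption. Item 3 attributes the audible alerts (below 100 and above 350 mg/dl) to the CGM device without saying which part sounds them. I take it to be the app on the phones. The loss of displayed readings does not depend on this.

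**The case against.** The strongest reply has four parts.

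- **Loose wording.** The phone sentence follows the one on removing the sensor, and it could mean that phones go back after the whole episode is over. This is possible but strained, because item 6 itself separates resolution from sensor removal and gives a reason for doing so. If it is what was meant, the sentence should say so.
- **The sensor still has some use.** A sensor left in place avoids a new insertion and the 2-hour warm-up described after item 2. Item 3 also implies an attempt to restore the signal before any ICU transfer. This stands in part: the benefit is delayed rather than lost, provided that someone brings phones back. The plan does not say that anyone will.
- **Limited danger.** A reopened gap is found from laboratory results, not by a phone, and hourly fingersticks are the written cover in the meantime. This also stands. The patient is not left without any glucose testing under the plan, although the plan elsewhere says that stepdown could not provide that testing.
- **No measured harm.** The number affected is unknown and no endpoint is touched. This is right, and it limits the weight of the point. It does not remove the inconsistency.

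**Conclusion.** The concern holds. Followed as written, item 6 leaves none of the three described receivers in place for the period in which the sensor is kept on for further monitoring. A patient whose gap reopened would have no displayed CGM reading until phones were brought back. The stated reason for leaving the sensor on is therefore not met by the plan as it stands.

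Only those of the 50 planned prospective patients whose gap reopens between resolution and sensor removal are affected, and that number cannot be derived from the documents. The conclusion assumes that the described route for readings is the complete one, and that phones are not re-issued by an unwritten practice. This is an operational and safety inconsistency that should be corrected. I claim no effect on the primary outcome, sample size, power, ICU stay, cost or hypoglycaemia counts.

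**What to change.** Replace the last sentence of item 6 with: the study smartphones are returned to the research coordinator when the sensor and transmitter are removed.

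Tying return to removal, with no list of removal times, also covers removal on ICU transfer (item 3) and before MRI or CT (item 4). If the staff information sheet covers phone return, its line should be changed to match.

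The cost is one protocol sentence and longer use of each set of three phones, from DKA resolution to sensor removal and never beyond 10 days from insertion. The documents do not say how many sets exist, so the team should check that supply allows this. If it does not, a written step for re-issuing phones promptly when the gap reopens would be a weaker substitute, since readings would still be missing until the phones arrived.
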